8.1.7.1. Dosing Schedule

The dose titration schedule below provides guidance regarding titration of subject dosing upon enrollment into the open label extension portion of the study following participation in the double-blind randomization.

- All subjects will be started on the weekly CAM2038 regimen during the open label extension.
- Subjects completing the randomized double-blind phase on 4 mg, 8 mg, or 12mg CAM2038/placebo q1w will continue the same dose of active treatment (open label CAM2038) without need for titration.
- Subjects completing the randomized double-blind phase on 64 mg, 96mg, or 128mg CAM2038/placebo q4w will begin open label treatment at the corresponding equivalent weekly dose last received by the subject prior to transition to the monthly dosing regimen. The subject may transition to monthly dosing upon return to the clinic in 1 week following the initial dose. At the investigator’s discretion, the transition period may be extended or the patient down-titrated, in case of poor tolerability.
- Additional details are presented in [Table 4](#) below:

Table 4 Open-Label Extension Dose Schedule for Randomized Double-Blind Rollover

Randomized Double-Blind Dose	Titration Schedule
4mg CAM2038 q1w	Remain at 4mg weekly
8mg CAM2038 q1w	Remain at 8mg weekly
2mg CAM2038 q1w	Remain at 12mg weekly
64mg monthly*	Start at 16mg q1w
96mg monthly*	Start at 24mg q1w
128mg monthly*	Start at 32mg q1w

*Please note:

- 16 mg CAM2038 q1w is the dosing equivalent of 64 mg CAM2038 q4w
- 24 mg CAM2038 q1w is the dosing equivalent of 96 mg CAM2038 q4w

- 32 mg CAM2038 q1w is the dosing equivalent of 128 mg CAM2038 q4w

8.2. Identity of Investigational Product(s)

The following treatments will be used during the study:

- CAM2038 (BPN FC Injection depot for q1w administration), 6.25 mg/mL: 4 mg (BPN base), 0.64 mL SC injection.*
- CAM2038 (BPN FC Injection depot for q1w administration), 50 mg/mL: 8 mg, 12 mg, 16 mg, 24 mg, and 32 mg (BPN base), 0.16, 0.24, 0.32, 0.48, and 0.64 mL SC injection.
- CAM2038 (BPN FC Injection depot for q4w administration), 356 mg/mL: 64 mg, 96 mg, and 128 mg (BPN base), 0.18, 0.27, and 0.36 mL SC injection.
- Placebo: 0.16, 0.32, 0.48 and 0.64 mL SC injections for q1w or q4w administration.

** CAM2038 6.25 mg/mL has been interchangeably referred to as CAM2048 during its development. The active ingredient is the same as for CAM2038 q1w. It also has the same excipients, as the CAM2038 q1w. For the purposes of this protocol, all reference to CAM2048 shall be considered to refer to and interchangeable with CAM2038 q1w*

8.2.1. Description of CAM2038 q1w, CAM2038 q4w, and Placebo SC Injection Products

CAM2038 q1w will be supplied as a pre-filled syringe with safety device and plunger containing the following: BPN, soybean phosphatidylcholine, glycerol dioleate, and anhydrous ethanol.

CAM2038 q4w will be supplied as a pre-filled syringe with safety device and plunger containing the following: BPN, soybean phosphatidylcholine, glycerol dioleate, and N-Methyl-2- pyrrolidone.

Placebo SC injections will be supplied as matching (for CAM2038 q1w) or nearly matching (by volume and color for CAM2038 q4w) pre-filled syringes with safety devices and plungers containing the following: soybean phosphatidylcholine, glycerol dioleate, and ethanol.

More information regarding the CAM2038 q1w and CAM2038 q4w and matching or nearly matching placebo injections can be found in the Instructions for User (IFU).

8.2.2. Description of the Buprenex Test Dose

Buprenex (BPN hydrochloride) will be sourced centrally and will be given as 1 mL deep IM injection corresponding to 0.3 mg BPN according to the prescribing information.

8.2.3. Description of the IR Morphine

Morphine sulfate IR will be supplied as 15-mg tablets for oral administration.

8.2.4. Description of the Hydrocodone/Acetaminophen

Hydrocodone/Acetaminophen will be supplied as 5 mg/325 mg for oral administration.

8.2.5. Handling, Storage, and Accountability

All study drugs will be transported, received, stored, and handled strictly in accordance with the container or product label, the instructions provided to the research site and applicable regulations.

The CAM2038 drug products, IR morphine, Buprenex, and hydrocodone/acetaminophen 5 mg/325 mg as rescue medication should be stored in a secured area at room temperature (59° to 77° F or 15° to 25° C) and in accordance with the product labeling and all applicable laws, regulations and local/institutional requirements.

Detailed drug accountability records must be maintained, including the dates shipments are received, the quantity of material received, the dates dispensed and the running inventory. The unused quantities will be returned to the Sponsor's drug supply vendor at the end of the trial. All unused supplies will be checked against the drug accountability records during the study and/or at the end of the study. Subjects will be instructed to return all unused study drugs to the clinical site. The investigator or designee must maintain an inventory record of all rescue medications dispensed to subjects.

Mishandling, potential theft, significant loss of clinical supplies at the site, or other suspected diversion must be reported to the Sponsor within 24 hours of first knowledge of the issue. If diversion is confirmed or suspected (e.g., excessive use of rescue medications), the study staff will be required to complete a clinical supply product complaint form, including documenting if a subject sold drug or gave drug to a friend or relative, if there was a discrepancy in drug accountability and suspected diversion, if a subject had drug stolen, or if there was diversion or theft by site staff or others.

BPN (Schedule III), morphine sulfate (Schedule II), and hydrocodone/acetaminophen 5 mg/325 mg (Schedule II) are controlled substances and must be handled and stored strictly in accordance with restrictions related to controlled substances. Study drugs must be kept securely locked with access limited to appropriate study personnel, according to applicable regulations.

8.2.6. Dispensing and Administration

Only eligible subjects participating in the study will receive the study drug. Only authorized research site staff may supply or administer the study drugs. Once dispensed, study drug may not be relabeled or reassigned for use by other subjects.

During the Double-Blind Phase, the pharmacist will be unblinded to the randomization code to permit dispensation of the CAM2038/placebo q1w and CAM2038/placebo q4w syringes to an unblinded staff member who will perform the injections. All other site study personnel, including the investigator and study coordinator, as well as the subjects, will remain blinded to treatment until the study is unblinded by the study sponsor. The unblinded staff member will be instructed not to discuss the trial with the blinded staff to ensure the blind is maintained.

Injections will be administered in different SC sites, to avoid injecting into the same exact site ([Appendix 2](#)). Detailed instructions for use will be provided in the IFU.

8.3. Method of Assigning Subjects to Treatment Groups

Randomization will be used to avoid bias in the assignment of subjects to treatments, to increase the likelihood that known and unknown subject attributes (e.g., demographics, baseline characteristics) are evenly balanced across treatment groups, and to enhance the validity of statistical comparisons across

treatment groups.

Subjects who provide written informed consent will be assigned a unique number in the screening process. This number will be used to identify the subject throughout the study.

Subjects who meet the eligibility criteria will be randomized in a 1:1 ratio (Group 1: active CAM2038 SC injections or Group 2: placebo SC injections). Randomization will be stratified based on double blind dosing regimen. Subjects randomized at a titration dose of either 4, 8 or 12 mg will remain on weekly doses. Subjects randomized at a titration dose of 16, 24, or 32 mg will transition to monthly dosing.

Therefore, there will be four different dose types.

- A1 – Active weekly
- B1 – Placebo weekly
- A4 – Active monthly
- B4 – placebo monthly

Due to the size of the study, it is expected that subjects will be balanced for various other baseline factors, including age.

Once any subject number or randomization number is assigned, it cannot be reassigned to any other subject. This study will use central randomization, as described in Section 9.2.

8.4. Selection of Dose

The study will include the following doses based on each subject's individual analgesia needs and tolerability:

- CAM2038 q1w 6.25 mg/mL: 4 mg (BPN base); 0.64 mL SC injection
- CAM2038 q1w 50 mg/mL: 8 mg, 12 mg, 16 mg, 24 mg, and 32 mg (BPN base); 0.16, 0.24, 0.32, 0.48, and 0.64 mL SC injection
- CAM2038 q4w, 356 mg/mL: 64 mg, 96 mg, and 128 mg (BPN base); 0.18, 0.27, and 0.36 mL SC injection.

Dose adjustments will be allowed during the Open Label Titration Phase only.

Rescue medication is oral hydrocodone/acetaminophen, 5 mg/325 mg tablets, q4-6 h prn. The maximum daily dose is 30 mg/1950 mg/day. Subjects cannot take more than one rescue tablet per day, on average, in the week prior to randomization.

On Day 1 of the Titration Phase, subjects will receive a test dose consisting of a single IM injection of 0.30 mg (1.0 mL) Buprenex and will be assessed for any changes in QTcF or withdrawal prior to any administration of CAM2038.

8.5. Selection and Timing of Dose

Subjects will be randomized to receive either CAM2038 or placebo at individualized doses. No fasting or special dietary requirements are required for the study.

8.6. Blinding

In order to reduce the potential for bias in the study, treatment group assignments will be double-blinded during the Double-Blind Phase. The subject, investigational site personnel, Sponsor, and Sponsor designees directly involved in the conduct and/or monitoring of this study will not be aware of the treatment group assignments.

There is a slight difference in color and fill volume between the placebo and active CAM2038 q4w; however, the viscosity is the same. In order to maintain the blind given the differences in color and fill volume, the following will be implemented during the Double-Blind Phase:

- The Injecting Clinician and any other staff involved in the injection process will not participate in subject evaluations, nor discuss any information regarding the injections with the subjects or other study staff.
- To keep the subjects blinded, appropriate steps will be taken to ensure that the subject is unable to view the syringe at any time.
- The study staff will not ask the Injecting Clinician or any other staff involved in the injection process for information regarding subject group assignment that might inadvertently unblind the study staff.

Under normal circumstances, the blind will not be broken until all participants have completed treatment. In case of emergency, and only if the information is required by the investigator to ensure subject's safety in managing a medical condition, the treatment may be unblinded at the site by using a code break module. The code break module will be provided by the Sponsor or designee. If possible, the investigator should contact the Sponsor prior to unblinding and after any actions have been taken. Whenever a treatment sequence is prematurely unblinded, the reason, date, and time of the unblinding and the individual who broke the blind must be documented. Individual code breaks will result in withdrawal of the subject from the study.

8.7. Prior and Concomitant Medications and Therapy

All non-study medications, including prescription, over-the-counter, or herbal therapies, used by the subject will be documented for the 30 days prior to Screening and throughout the study. The investigator will determine if the prior/concomitant medication(s) affect the subject's eligibility to participate or continue to participate in the study. The following restrictions on concomitant medications will be in place during the study:

- Opioid receptors are likely to be occupied by BPN, which may reduce the analgesic effects of an opioid. The dissociation of BPN from the receptors may take up to 2 weeks (for CAM2038 q1w) or at least 2 months (for CAM2038 q4w) following the last CAM2038 injection. Therefore, subjects requiring analgesic emergency treatment or anesthesia for surgery should ideally be treated with a non-opioid analgesic. Opioids may be used with caution, but as higher doses may be required for analgesic effect, there may be a higher potential for toxicity with opioid administration. The clinical course should be carefully evaluated and fully documented for subjects who have a requirement for any opioid analgesic for >7 days continually or general anesthesia for surgery.

BPN is metabolized via CYP3A4. Because CYP3A4 inhibitors may increase plasma concentrations of BPN, CYP3A4 inhibitors such as azole antifungals (e.g., ketoconazole), macrolide antibiotics (e.g., erythromycin), and HIV protease inhibitors (e.g., ritonavir, indinavir, and saquinavir) are prohibited for at least 30 days prior to Screening. Interactions with CYP3A4 inducers have not been investigated; therefore, CYP3A4 inducers (e.g., phenobarbital, carbamazepine, phenytoin, and rifampicin) are prohibited for at least 30 days prior to Screening.

- Concomitant use of other narcotic anesthetics, benzodiazepines, phenothiazines, other tranquilizers, or other central nervous system (CNS) depressants (including alcohol and sedative/hypnotics) may cause respiratory and CNS depression. Use of these substances should be minimized during treatment with CAM2038. If these sedatives are required during the study, the Medical Monitor must be consulted. Subjects should be advised of the danger of concomitant use of sedatives while participating in the study. Subjects should be explicitly advised of the danger of IV abuse of benzodiazepines and abuse of alcohol while under treatment with CAM2038.

The following concomitant medications and therapies may be permitted during the study:

- Nonsteroidal anti-inflammatory drugs will be permitted occasionally for headache, fever, or other indications, aside from CLBP, for no more than 3 consecutive days and no more than the maximum daily recommended dose
- Other non-opioid analgesics are permitted, but subjects must be on a stable dose ($\pm 20\%$ dose and timing of administration) for at least 30 days prior to enrollment
- Rescue medication
- Anti-constipation medications
- Aspirin at doses ≤ 325 mg/day for cardiovascular prophylaxis

The following medications and therapies are permitted, but must remain stable ($\pm 20\%$ dose and timing of administration) throughout the duration of the subject's participation in the study:

- Muscle relaxants
- Hypnotics (eszopiclone, zolpidem, zaleplon)
- Antidepressants
- Anticonvulsants
- Physical therapy
- Biofeedback therapy
- Acupuncture therapy
- Herbal remedies (except products that can affect CYP3A4, such as St. John's Wort)

On a case-by-case basis, the investigator is permitted to allow the use of some concomitant medications, for example, to treat an AE, as long as the investigator determines that the medication will not affect the subject's safety or study integrity (e.g., topical medications). Wherever possible, the investigator should obtain approval from the Sponsor's Medical Monitor prior to administering the medication.

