9. A nerve or plexus block, including epidural steroid injections or facet blocks, within 1 month prior to Screening or botulinum toxin injection in the lower back region within 3 months of Screening.
10. History of chemotherapy or confirmed malignancy (except basal cell carcinoma) within the past 2 years.
11. Any other acute or chronic pain condition that could interfere with the subject’s ability to report their CLBP accurately and consistently and/or interfere with the study staff’s ability to assess the subjects CLBP.
12. An active or pending workman’s compensation, insurance claim, or litigation related to back pain (i.e., primary claim is back pain).
13. Clinically significant history, in the opinion of the investigator, of suicidal ideation or current evidence that the subject is actively suicidal.
14. Clinically significant history of major depressive disorder that is poorly controlled with medication, per investigator judgment.
15. Hypersensitivity or allergy to BPN, other opioids, or excipients of CAM2038.
16. Hypersensitivity or allergy to acetaminophen.
17. Use of strong inhibitors or inducers of cytochrome P450 3A4 (CYP3A4), such as some azole antifungals (e.g., ketoconazole), macrolide antibiotics (e.g., clarithromycin), or protease inhibitors (e.g., ritonavir, indinavir, and saquinavir) within the 30 days prior to Screening.
18. Use or planned use of natural supplements that can affect CYP3A4, such as St. John’s Wort, throughout the study.
19. Has a major bleeding disorder, such as hemophilia, or treated with high levels of anticoagulants per the investigator’s discretion.
20. Current or confirmed past diagnosis of Sphincter of Oddi dysfunction.

21. Has a significant hepatic disease, as indicated by Screening clinical laboratory assessment results (aspartate aminotransferase, alanine aminotransferase, or lactate dehydrogenase values $\geq 3 \times$ the upper limit of normal [ULN]) or has a creatinine value $\geq 1.5 \times$ ULN).
22. Is an employee of the investigator or the trial site, with direct involvement in the proposed trial or other studies under the direction of the investigator or trial site or is a family member of the investigator or of an employee of the investigator.
23. Has any pending legal action that could prohibit participation or compliance in the study.

Criteria for Entry into the Titration Phase:

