13. Clinically significant history, in the opinion of the investigator, of suicidal ideation or current evidence that the subject is actively suicidal.
14. Clinically significant history of major depressive disorder that is poorly controlled with medication, per investigator judgment.
15. Hypersensitivity or allergy to BPN, other opioids, or excipients of CAM2038.
16. Hypersensitivity or allergy to acetaminophen.
17. Use of strong inhibitors or inducers of cytochrome P450 3A4 (CYP3A4), such as some azole antifungals (e.g., ketoconazole), macrolide antibiotics (e.g., clarithromycin), or protease inhibitors

- (e.g., ritonavir, indinavir, and saquinavir) within the 30 days prior to Screening,
18. Use or planned use of natural supplements that can affect CYP3A4, such as St. John's Wort, throughout the study.
 19. Has a major bleeding disorder, such as hemophilia, or treated with high levels of anticoagulants per the investigator's discretion
 20. Current or confirmed past diagnosis of Sphincter of Oddi dysfunction.
 21. Has a significant hepatic disease, as indicated by Screening clinical laboratory assessment results (aspartate aminotransferase, alanine aminotransferase, or lactate dehydrogenase values $\geq 3 \times$ the upper limit of normal [ULN]) or has a creatinine value $> 1.5 \times$ ULN).
 22. Is an employee of the investigator or the trial site, with direct involvement in the proposed trial or other studies under the direction of the investigator or trial site or is a family member of the investigator or of an employee of the investigator.
 23. Has any pending legal action that could prohibit participation or compliance in the study.

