9. STUDY PROCEDURES AND ASSESSMENTS

All study assessments will be performed at the visits and time points outlined in the Schedule of Assessments ([Table 5](#), [Table 6](#), and [Table 7](#)). Open-label safety extension assessments for existing subjects enrolled from the randomized Double-Blind Phase is present in [Table 8](#). [Table 9](#) and [Table 10](#) presents the schedule of assessments for de novo subjects in Open Label Safety Extension Phase. The following sections outline the details and procedures associated with the assessments.

Table 5: Schedule of Assessments for Screening, Transition, and Titration Phases

Study Period/Phase:	Screening	Transition Phase ¹		Open-Label Titration Phase ²									
	Week: W-2 to -1	W0		W1	W2	W3	W4	W5	W6	W7	W8	W9	W10
Day:	D-14 to -1	D1 up to 10-12 days ³	2 to 4 days										
Informed Consent ⁴	X												
Eligibility Criteria Review	X			X ⁵									
Demographic Data	X												
Medical and Medication History	X												
Physical Examination ⁶	X												
Vital Signs ⁷	X			X ⁸	X	X	X	X	X	X	X	X	X
ECG	X			X ^h	X	X	X	X	X	X	X	X	X
Clinical Laboratory Assessments	X			X				X ⁹					
Pregnancy Test ¹⁰	X			X		X		X		X		X	
Hepatitis B/C, HIV ¹¹	X												
Urine Drug Screen	X			X	X	X	X	X	X	X	X	X	X
Dispense Treatment Identification Card				X									
Down-Titrate Opioid Dose		X											

¹ Subjects on BPN at screening will participate in the down titration but will not transition to morphine IR. Subjects will washout and refrain from their BPN treatment for 12-24 hours prior to the test dose on Day 1.

² Titration Phase visit window is ±3 days.

³ Telephone contact.

⁴ Subjects must voluntarily provide written informed consent prior to any study-related procedures being performed.

⁵ Prior to starting the Titration Phase, all Inclusion/Exclusion and other relevant criteria must be met.

⁶ A complete physical examination of all major body systems (including height, weight, and BMI) will be performed.

⁷ Includes body temperature, blood pressure, pulse rate, pulse oximetry and respiration rate.

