^c This visit is defined as the twelfth week of the Double-Blind Phase in the analyses of data.

^d Telephone contact only.

^e Prior to enrollment into the Double-Blind Phase, all Inclusion/Exclusion and other relevant criteria must be met.

^f A complete physical examination of all major body systems (including height, weight, and BMI) will be performed.

^g Includes body temperature, blood pressure, pulse rate, pulse oximetry and respiration rate and will be performed at every visit, prior to treatment, and 1-hour post-study treatment (allowable window of 60-90 minutes).

^h ECGs will be assessed at Week 11, prior to treatment and 1-hour post-dose (allowable window of 60-90 minutes).

ⁱ A serum pregnancy test will be performed at the Final Study Visit/Early Termination. An “in-office” urine pregnancy test will be required weekly (for women of childbearing potential).

^j COWS/SOWS will be assessed before dosing.

^k Subjects who are receiving 4 mg, 8 mg or 12 mg CAM2038 q1w will randomize to CAM2038/placebo q1w with weekly injections throughout the Double-Blind Phase.

^l Rescue medication will not be dispensed at this visit.

Study Period/Phase:	Double-Blind Phase ^{ab}												Final Study Visit ^c	Follow-up Phase ^d
Month:	M4				M5				M6					M7
Week:	11	12	13	14	15	16	17	18	19	20	21	22	23	27
Daily Electronic Diary Pain Rating (NRS-11)	X	X	X	X	X	X	X	X	X	X	X	X	X	
EQ-5D-5L	X				X				X				X	
WPAI	X				X				X				X	
C-SSRS ^m	X				X				X				X	
CGI-I Scale	X				X				X				X	
PGI-I Scale	X				X				X				X	
Concomitant Medications/Procedures	X	X	X	X	X	X	X	X	X	X	X	X	X	X
Adverse Events ⁿ	X	X	X	X	X	X	X	X	X	X	X	X	X	X
Adjust Opioid Treatment													X ^o	

BMI=Body Mass Index; CGI-I=Clinical Global Impression Improvement; C-SSRS=Columbia Suicide Severity Rating Scale; COWS=Clinical Opiate Withdrawal Scale; ECG=electrocardiogram; EQ-5D-5L=EuroQoL Group 5-dimension 5-level self-report questionnaire; ET=Early Termination; NRS-11=11-point numerical rating scale; PGI-I=Patient Global Impression of Improvement; q1w=once weekly; q4w=once monthly; SC=subcutaneous; SOWS=Subjective Opiate Withdrawal Scale; WPAI=Work Productivity and Activity Impairment.

^m Since Last Visit' version to be used.

ⁿ Any spontaneously reported AEs will be recorded after the subject signs the ICF. In addition, AEs will be elicited using a non-leading question each time the subject visits the clinic.

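### Section 8.7 presents its ban on CYP3A4 inhibitors and inducers as an on-study restriction, but the stated window ends at Screening, before any CAM2038 is given

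*Protocol*

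**What the plan says.** Protocol Section 8.7 introduces its list with "The following restrictions on concomitant medications will be in place during the study". Three drug groups follow: opioids, CYP3A4 inhibitors and inducers, and sedatives or other CNS depressants.

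The CYP3A4 paragraph gives its reason first: "Because CYP3A4 inhibitors may increase plasma concentrations of BPN". It then says that azole antifungals, macrolides and "HIV protease inhibitors (e.g., ritonavir, indinavir, and saquinavir) are prohibited for at least 30 days prior to Screening". For inducers (phenobarbital, carbamazepine, phenytoin and rifampicin are named) it says that interactions have not been investigated, and it sets the same window. Exclusion 17, in the synopsis and in Section 7.2, excludes strong inhibitors or inducers over the 30 days before Screening.

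Neighbouring rules are worded differently. Exclusion 18 covers "Use or planned use of natural supplements that can affect CYP3A4" and runs for the whole study. The sedative bullet of Section 8.7 says: "If these sedatives are required during the study, the Medical Monitor must be consulted".

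**The concern.** A prohibition meant to protect subjects from a drug interaction has to cover the time when both drugs can be present. Read literally, this one covers only the time before Screening.

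The likely case is a new infection during treatment. HIV infection is an exclusion, so the protease inhibitors are not realistic. That leaves the azole antifungals, the macrolides and rifampicin. One site could follow the stated window and start the drug. Another could follow the lead-in and refuse it, or discontinue the subject. Both could cite Section 8.7.

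Two design features make it harder to correct a problem afterwards. Section 4.1.2 describes release over 4 weeks from a monthly injection, so exposure cannot be stopped at once. Section 8.4 allows dose adjustment only in the Open Label Titration Phase.

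**Working it through.** There is no planned figure to reproduce. The check sets the rules side by side.

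| Protocol text | Drugs covered | Period stated |
|---|---|---|
| 8.7, lead-in | the whole list | during the study |
| 8.7, inhibitor sentence | CYP3A4 inhibitors, no potency limit | at least 30 days before Screening |
| 8.7, inducer sentence | CYP3A4 inducers, no potency limit | at least 30 days before Screening |
| Exclusion 17 (synopsis, 7.2) | strong inhibitors or inducers | 30 days before Screening |
| Exclusion 18 (synopsis, 7.2) | natural supplements affecting CYP3A4 | throughout the study |
| 8.7, herbal line of the stable-use list | herbal remedies, except those affecting CYP3A4 | throughout participation |
| 8.7, sedative bullet | CNS depressants | during treatment, consultation mandatory |
| 7.5.2, rollover to the extension | no mention of CYP3A4 | not applicable |

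1. *Timing.* Screening lasts up to 2 weeks and Transition up to 2 weeks (Section 6.1). The first CAM2038 injection is on Day 1 of Titration. The stated window therefore closes up to about 2 + 2 = 4 weeks before the first dose. It does not reach a drug started during Screening or Transition, nor one started later.

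2. *Purpose.* Section 8.7 justifies the inhibitor ban by buprenorphine concentration. For CAM2038 that can matter only after an injection. The remark that inducer interactions have not been investigated is likewise a reason for caution on treatment.

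3. *Later checks.* Table 5 says "Prior to starting the Titration Phase, all Inclusion/Exclusion and other relevant criteria must be met", and Table 6 says "Prior to enrollment into the Double-Blind Phase, all Inclusion/Exclusion and other relevant criteria must be met". Applying exclusion 17 again at those visits tests the same 30 days before Screening, so it would not detect a later start. Subjects rolling over from the Double-Blind Phase meet one general exclusion (Section 7.5.2), which rests on the investigator's opinion.

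4. *Drafting contrast.* Exclusion 18 shows that the authors wrote an on-study period when they wanted one. As worded, St. John's Wort is expressly barred on treatment and ketoconazole is not. The anticonvulsant line of the stable-use list has no CYP3A4 exception, although three of the four named inducers (phenobarbital, carbamazepine, phenytoin) are anticonvulsants.

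5. *What remains on study.* Apart from the lead-in, the controls after Screening are general. The investigator decides whether a medication affects continued participation (8.7). A case-by-case clause lets the investigator allow some medications if safety and study integrity are unaffected, with Medical Monitor approval sought where possible (8.7). Discontinuation for unacceptable concomitant medication is optional (7.7). None of these names the CYP3A4 drugs, and none is as firm as the sedative rule.

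**The case against.** The strongest reply is that the ban already applies on study. The drugs sit under a lead-in that says so, the words *at least* can be read as the minimum washout at which the restriction begins, and the stated reason makes sense only on treatment. Azoles, macrolides and rifampicin are also absent from the permitted list in Section 8.7. The natural route for them is therefore the case-by-case clause, whose own example is treating an adverse event. In the Double-Blind Phase, concomitant medications are reviewed at every visit, and pulse oximetry and respiration rate are measured at every visit (Tables 6 and 7). Section 4.2 cites a ceiling effect on respiratory depression.

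Much of this stands. It makes the point an internal conflict with partial safeguards and lowers the severity. It does not remove the point, because the operative sentences still state a period that ends at Screening. If the lead-in gives the true intent, the edit simply records it.

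A reader might infer three stronger claims that the documents do not support:

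- *No rule at all applies on treatment.* The lead-in and the discretionary controls contradict this.
- *A measured gap, such as 0 of 22 injection weeks covered (10 titration + 12 double-blind).* This restates the literal reading and does not measure exposure. On the lead-in's reading all 22 weeks are covered.
- *A QT hazard, because several named inhibitors are also in Appendix 1.* Section 8.7 gives buprenorphine concentration as its reason, not QT. Appendix 1 is broad: it includes diphenhydramine, famotidine, pantoprazole and sertraline. Exclusion 8 keeps out users of such drugs only if the screening ECG is also clinically abnormal. Overlap with that list shows nothing particular to CYP3A4 drugs.

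**Conclusion.** The point holds as a conflict within Section 8.7. The lead-in points to an on-study restriction, while the two CYP3A4 sentences and exclusion 17 state a window that ends before any CAM2038 is given. The stated window does not serve the stated purpose, and the general controls leave the decision to each site.

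Severity is minor to moderate. The documents give no rate of use of these drugs and no size of change in buprenorphine level, so no count of affected subjects and no effect on the efficacy comparison is claimed. The conclusion rests on the text alone. It assumes only that some subjects may need a new anti-infective or other CYP3A4-active medicine after Screening.

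**What to change.** In both CYP3A4 sentences of Section 8.7, replace the present period with *from at least 30 days prior to Screening and throughout the study*. Leave the drug wording as it is. In particular, do not add *strong*: that qualifier appears only in exclusion 17, and adding it to Section 8.7 would narrow the present ban.

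Add one sentence modelled on the sedative rule: *If such a drug becomes clinically necessary during the study, the Medical Monitor must be consulted.* This makes consultation mandatory for these drugs and keeps a route open for needed treatment.

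Optionally, add *or planned use during the study* to exclusion 17 in the synopsis and Section 7.2, to match exclusion 18. This is for consistency only, since it would not catch an unplanned new illness.

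The cost is two edited sentences and one new one in a single protocol amendment, plus the optional change in two places. The SAP and the sample size do not change. The downside is that a few subjects may need an alternative anti-infective or may be discontinued.
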